- 21) Hypertension with systolic BP >160 mm Hg or diastolic BP >90 mm Hg at screening, systolic BP > 165 mm Hg or diastolic BP > 95 mm Hg immediately prior to treatment with study drug or hypotension with systolic BP < 90 or diastolic < 60 at screening or immediately prior to treatment with study drug; heart rate >110 or <60 at either of these time points;
- 22) Treatment with sildenafil (Viagra), tadalafil (Cialis), Avanafil (Stendra), Vardenafil (Levitra) or other drugs in the same category of phosphodiesterase-5 enzyme inhibitors within 2 weeks of infusion.

In no case will it be recommended to a participant to discontinue a particular treatment if there is any evidence that the treatment is providing clinical benefit. Additionally, only the patient's prescribing physician, and never the study physician, will take a patient off a medication.

If urine toxicology is positive and not explained by a prescribed medication at any point during the study, the participant will be disqualified from the study. If this occurs, the patient will be provided with a referral for drug counseling and treatment if the patient wishes to seek treatment.

As part of the initial screening, subjects will be asked to provide emergency contact information, and their consent obtained to call the emergency contact to confirm that they are willing and able to serve as such.

Finally, a capacity evaluation will be conducted by an independent psychiatrist in order to ensure sufficient subject understanding of the potential risks and benefits of participating in the study.

 Mount Sinai	Protocol Title:	Pharmacologic attenuation of ketamine using nitroprusside
	Principal Investigator Name/Contact Info:	[name]/ [contact]
	Primary Contact Name/Contact Info	[name] / [contact]
	Date Revised:	4/15/2019
	Study Number:	HSM#16-00928/GCO#16-1580

c) Number of Subjects

Our goal is for 40 individuals to be randomized in this study. Based on our expected screen fail rate, we expect to enroll approximately 100 patients who will sign the consent for and be screened for study eligibility.

d) Study Timelines

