Subjects undergo a screening period that may last up to four weeks (Visit 0). Eligible subjects then undergo the PLC/KET Test Infusion (Visit 1) and undergo evaluation of treatment response 24 hours following the infusion (Visit 2). For subjects who meet criteria to continue in the study, they are randomized to one of two treatment conditions (PLC/KET or NP/KET) to take place up to four weeks from the Test Infusion (Visit 3). Subjects will again return for evaluation 1 week (+/- 2 days) following Visit 1(Visit 2a). After the second infusion (Visit 3), subjects will return for evaluation at 24 hours (Visit 4) and 1 week (+/- 2 days) following Visit 3 (Visit 5). Subjects will return for a final exit visit (Visit 6) 14 days (+/- 2 days) following the second infusion (Visit 3). Therefore, the total study participation time will be up to 10 weeks.

We anticipate a 2-year project period, during which time approximately 100 patients will be screened, with 40 patients randomized. However, after 8 patients have completed the study, the results will be unblinded to an independent statistician and an interim analysis conducted. On this basis, the study may be terminated, or it may be continued towards the goal of randomizing 40 total patients. A second interim analysis will be conducted once the sample size has doubled, and 16 patients have completed the study. The statistician will receive de-identified coded data only.

e) Study Endpoints

Primary Outcomes

- (a) Change in Montgomery–Asberg Depression Rating Scale (MADRS) compared across PLC/KET and NP/KET administrations.
- (b) Change in four-item positive symptom subscale of the Brief Psychiatric Rating Scale (BPRS), Clinician-Administered Dissociative States Scale (CADSS) and Visual Analog Scale (VAS) scores from Time 0 to Time 40 minutes compared across PLC/KET and NP/KET administrations.

 Mount Sinai	Protocol Title:	Pharmacologic attenuation of ketamine using nitroprusside
	Principal Investigator Name/Contact Info:	[name]/ [contact]
	Primary Contact Name/Contact Info	[name] / [contact]
	Date Revised:	4/15/2019
	Study Number:	HSM#16-00928/GCO#16-1580

Secondary Outcome

Change in molecular profiles obtained from blood draws of subjects at set time points that parallel clinical ratings during infusions of the agents under investigation and post-infusion follow up.

Statistical Analysis

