The null hypotheses of this study are that (a) pre-treatment with NP does not attenuate the antidepressant effects of KET (b) pre-treatment with NP does not reduce psychotic rating scores induced by KET, and (c) there are no changes in molecular measurements over the course of KET and/or NP infusions that correlate with clinical ratings. These hypotheses will be tested against their corresponding alternatives, namely that pre-treatment with NP effectively attenuates both the antidepressant and pro-psychotic effects of KET and that molecular changes in reflecting real-time changes in mental status can be tracked using serial blood draws.

Data will be analyzed using repeated measures General Linear Models with Time and Treatment Condition as within-subject variables. Overall F tests for significance will be followed up by post-hoc t-tests comparing rating scores between the treatment conditions.

The statistician will receive de-identified coded data only.

f) Procedures Involved in the Human Research

The current protocol consists of 8 study visits, as well as a phone call check-in (Study Visit 0: Screening; Study Visit 1: PLC/KET infusion; Study Visit 2: 24-hour follow-up of Study Visit 1; Study Visit 2a: 7-day follow-up of Study Visit 1; Phone-call follow-up of Study Visit 1; Study Visit 3: PLC/KET or NP/KET infusion; Study Visit 4: 24-hour follow-up of Study Visit 3; Study Visit 5: 7-day follow-up of Study Visit 3; Study Visit 6: study exit evaluation). Below, we first outline procedures for study drug administration that apply to both Study Visits 1 and 3. Then, we describe in more detail the procedures that will occur on each of the Study Visits. See Table 1 for an outline of the events occurring at all visits.

Description of Study Drug Procedures

 Mount Sinai	Protocol Title:	Pharmacologic attenuation of ketamine using nitroprusside
	Principal Investigator Name/Contact Info:	[name]/ [contact]
	Primary Contact Name/Contact Info	[name] / [contact]
	Date Revised:	4/15/2019
	Study Number:	HSM#16-00928/GCO#16-1580

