Study drugs are administered on Study Visits 1 (single-blind) and 3 (double-blind). Visits 1 and 3 will occur up to four weeks apart to allow subject depression levels to return to baseline, a necessary component of the study design in order to test whether NP has any effect on the antidepressant action of KET. At Visit 1, participants will receive single-blind placebo (PLC) followed by KET (0.5 mg/kg/hour for 40 minutes), in which they are blind to the PLC/NP condition but are aware they are receiving KET. Subjects return to the clinic 24 hours following Visit 1, at which time their eligibility to continue and be randomized in the study is determined. The criteria for continuing is a significant antidepressant response to KET as demonstrated by MADRS score of $\geq 50\%$ improvement from baseline. Eligible subjects are randomized to one of two treatment conditions for Visit 3 (double-blind): PLC/KET or NP/KET (NP dose: 0.5 micrograms/kg/minute for 240 minutes), where again, the blinded condition is PLC/NP, but the subjects are aware they are receiving KET. Ineligible subjects (i.e., ketamine non-responders) will be scheduled to return to the clinic for an exit visit 1 week (7 ± 2 days) following the first infusion. The appearance of the nitroprusside will be protected to allow this drug to be blinded. Given the potential lengthy duration between visits (between 2 and 4 weeks), subjects will return to the clinic approximately 1 week (7 ± 2 days) following V1 (PLC/KET) for a check-in (Visit 2a) with the study doctor in order to ensure subject safety, as well as to be evaluated for remission of depressive symptoms. Additionally, a phone call MADRS will be administered 3 to 4 days following the in-person check-in, which will serve as the final determinant of the subject's return to baseline (defined as receiving a score within 20% of the baseline MADRS). If the subject has not returned to baseline, the V3 will be rescheduled for a date approximately two weeks following its initial appointment in order to allow maximum time (4 weeks) for a return to baseline, and the two check-ins (Visit 2a and by-phone check-in) will be repeated for the next two weeks, for a total of 4 additional check-ins. Following the V3 infusion visit, subjects again return to the clinic at 24 hours (Visit 4) and at 7 ± 2 days (Visit 5) following the second infusion day, and once more 14 ± 2 days after the infusion for the Exit Visit (Visit 6).

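### Primary outcome (a) names no visit and no deciding F test, so the MADRS result depends on an unstated choice; one prespecified 24-hour contrast would settle it

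*Combined protocol and SAP*

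**What the plan says.** Section 5e, Primary Outcomes, gives (a) as change in "Depression Rating Scale (MADRS) compared across PLC/KET and NP/KET administrations". It names no starting score, visit or summary over visits. Outcome (b), listed next, does have a window: "scores from Time 0 to Time 40 minutes compared across PLC/KET and NP/KET administrations".

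The Statistical Analysis paragraph of the same section covers both outcomes: "Data will be analyzed using repeated measures General Linear Models with Time and Treatment Condition as within-subject variables". Then: "Overall F tests for significance will be followed up by post-hoc t-tests comparing rating scores between the treatment conditions". The levels of Time are not listed. The deciding F (treatment main effect or treatment-by-time interaction), the times of the t-tests, alpha and sidedness are not stated.

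After the randomised infusion, Sections 5d and 5f schedule Visit 4 (24 hours), Visit 5 (day 7) and Visit 6 (day 14). The visit descriptions name MADRS at Visit 5; for Visits 4 and 6 they mention only efficacy assessments.

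Two features of Section 5f bear on timing. Ketamine response is defined at 24 hours, as a MADRS improvement of at least 50%, and decides who is randomised. The design also expects that response to fade: "Visits 1 and 3 will occur up to four weeks apart to allow subject depression levels to return to baseline". Return to within 20% of baseline is judged by a telephone MADRS 3 to 4 days after the day-7 check-in, so at about day 10 to 11, with up to four weeks allowed.

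**The concern.** Aim I asks whether nitroprusside changes ketamine's antidepressant effect. By the protocol's own criterion that effect is measured at 24 hours, and by its own washout logic it shrinks afterwards. An F over several visits answers a different question. The treatment main effect averages over visits where there may be little left to attenuate. The interaction asks whether the arm difference varies over time in any direction, which is not the same as less improvement at 24 hours. The post-hoc t-tests do not repair this, because they come after the F and no visit is named.

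Two things are at stake. A real blunting at 24 hours could be missed if the treatment F is read. And because either F, or a t-test at any visit, could be presented as the primary result, the false-positive rate is not fixed. The same open choice applies at the interim analyses after 8 and 16 completers.

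**Working it through.** **Plan's own figure.** "Our goal is for 40 individuals to be randomized in this study" is a goal without a sample-size calculation. No alpha, power, effect size or SD is given, so it cannot be reproduced.

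**Inputs from the documents.** 40 randomised, two arms, follow-up at 24 hours, day 7 and day 14.

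**Assumptions.** 1:1 allocation (20 per arm), two-sided 5%, no dropout, equal correlation r between visits of 0.3 to 0.7, all three follow-up visits in the model, and a comparison between randomised arms.

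**Step 1: reference contrast.** For a two-sample t-test on 38 df, power is 80% at d = 0.909 (noncentrality 0.909 × √(20/2) = 2.87). The normal approximation gives (1.960 + 0.842) × √(2/20) = 0.886. The 24-hour effect is fixed at 0.909 SD of change, so the 24-hour contrast has 80% power by construction.

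**Step 2: two layouts.** Let p be the fraction of the effect present at each visit.
- Layout A, post-infusion changes only (3 levels, SD 1). Treatment F: d = 0.909 × mean(p) / √((1 + 2r)/3). Interaction: λ = 10 × 0.909² × Σ(p − mean p)² / (1 − r), on 2 and 76 df.
- Layout B, raw scores with baseline as a level (4 levels, SD 1, 24-hour effect 0.909 × √(2(1 − r))). Treatment F: d = 0.909 × √(2(1 − r)) × mean(p) / √((1 + 3r)/4). Interaction: λ = 16.53 × Σ(p − mean p)², on 3 and 114 df, free of r.

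Example, layout B, r = 0.3, effect at 24 hours only: 0.909 × √1.4 = 1.076. Divided by 4 this is 0.269. The SD of a patient's average is √(1.9/4) = 0.689, so d = 0.390 and power is 22.5%.

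Example, layout A, r = 0.3, half the effect left at day 7: 0.909 × 1.5/3 = 0.455. Dividing by √(1.6/3) = 0.730 gives d = 0.622 and power 48%.

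**Step 3: power (left figure r = 0.3, right figure r = 0.7).**

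| Effect at 24 h, day 7, day 14 | Treatment F, A | Treatment F, B | Interaction F, A | Interaction F, B |
|---|---|---|---|---|
| 1, 0, 0 | 25% to 18% | 22.5% to 9.5% | 69% to 97% | 84% |
| 1, 0.5, 0 | 48% to 35% | 44% to 15% | 56% to 91% | 80% |
| 1, 1, 1 | 97% to 88% | 95% to 46% | 5% | 84% |

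Simulation agrees with these to within sampling error.

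**Step 4: sensitivity.** With autoregressive correlation 0.7, baseline included and wear-off by day 14, simulation gives the treatment F 11% to 17% and the interaction F 65% to 70%. In a literal within-subject layout (20 patients with both conditions; baseline, 24 hours and day 7; effect at 24 hours only), the treatment F has 63% with no subject-by-condition variance. It falls to 34%, 21% and 14% as that variance rises to 0.4, 1 and 2 times the error variance. The interaction F stays at 84%. With half the effect left at day 7 and no such variance, the treatment F has 93%.

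**Step 5: type I error.** Under equal correlation the two Fs use independent parts of the data (patient averages and within-patient deviations). Accepting either gives 1 − 0.95² = 9.75%; simulation gives 9.6% to 9.9%. Accepting a 24-hour t-test as well gives about 11.5% to 13%.

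**The case against.** A reader might infer that the plan tests outcome (a) over visits where the ketamine effect is known to be gone, so that power will collapse. The documents do not support that much.

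- No text says that day 7 and day 14 are levels of Time. Inclusion is the natural reading, since Time is a factor and no visit is excluded, but it is an inference. If Time meant only pre-infusion and 24 hours, the interaction F would be the 24-hour change contrast itself.
- The loss belongs to the treatment main effect under wear-off. With baseline as a level and equal correlation, the interaction F has 80% to 84%, including when attenuation is constant. Its 5% figure arises only when post-infusion changes alone are modelled.
- If the effect persists fully to day 14, the treatment F can beat the 24-hour contrast.
- Little or no effect at day 7 is not stated anywhere. The return-to-baseline check supports wear-off by about day 10 to 14, and even then up to four weeks is allowed. Randomised patients are selected responders.
- The plan calls Treatment Condition within-subject, while the main figures compare arms. But "Eligible subjects are randomized to one of two treatment conditions for Visit 3 (double-blind): PLC/KET or NP/KET" means that patients allocated to PLC/KET never receive nitroprusside, so the randomised comparison is between arms. That mismatch is a separate matter.
- Aim I is worded broadly enough to include durability, so giving later visits primary weight would be defensible if it were stated.

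All of this limits the size of the claim. None of it supplies the missing visit, the levels of Time or the deciding F. That the answer changes with each of these choices is the defect.

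**Conclusion.** The point holds in this form: primary outcome (a) has no defined time point, and the test that decides it is not identified. If later visits enter the model and the effect wears off by day 14, the treatment F has about 10% to 48% power where a 24-hour contrast has 80%. The treatment-by-time F may match or exceed the contrast, but it is non-directional and does not itself show attenuation at 24 hours. Under full persistence the treatment F has 46% to 97%. Treating either F as primary roughly doubles a 5% type I error.

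These figures rest on an assumed effect size, correlation, alpha, allocation ratio and decay pattern, because the protocol gives none of them. They show how far the result depends on an unstated choice; they do not predict this trial's power. Adding a date alone would not be enough, because a 24-hour t-test that is still gated on an overall F keeps most of the problem. The change should be made; it does not call the trial's design into question.

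**What to change.** In Section 5e, define primary outcome (a) as MADRS change from the Visit 3 pre-infusion score to Visit 4 (24 hours). Test it between randomised arms by one single-degree-of-freedom contrast from a baseline-adjusted model, at a stated alpha and sidedness and not conditional on any overall F. List the visits in the model, name MADRS among the Visit 4 assessments, and make day 7 and day 14 secondary.

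One detail must be settled with it. Section 5f says that infusion days use a modified MADRS without the sleep and appetite items. That is 8 items with a maximum of 48, against 10 items and 60 for the full scale. The change must be computed on the same items at both visits.

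The cost is wording only: no new visits or patients. The downside is that an effect seen only at day 7 or 14, or the extra power from averaging a persistent effect, becomes secondary. If the investigators regard durability as part of Aim I, they should say so and prespecify a single summary for it.

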Each treatment day (Visit 1 and 3) involves Infusion 1 (PLC or NP) and Infusion 2 (KET). Prior to Infusion 1 (PLC on Study Visit 1; PLC or NP on Study Visit 3) an indwelling catheter will be placed in the antecubital veins of each arm, and pulse, blood pressure, pulse-oximetry, and an EKG strip will be placed for continuous vital monitoring, which will be performed throughout the infusions. One of these catheters will be used for the administration of NP/PLC, and one will be used for the administration of KET; this is to ensure no interaction effects between the drugs given in the same line. At Time 0, Infusion 1 will begin through an infusion pump and will continue until Time 240 minutes. At Time 200

Protocol Title:	Pharmacologic attenuation of ketamine using nitroprusside
Principal Investigator Name/Contact Info:	[name]/ [contact]
Primary Contact Name/Contact Info	[name] / [contact]
Date Revised:	4/15/2019
Study Number:	HSM#16-00928/GCO#16-1580

minutes, Infusion 2 (KET on both Study Visits 1 and 3) will begin and will continue until Time 240 minutes, at which point all medication administration will be complete for the Study Visit. Clinical ratings (BPRS, CADSS, VAS; see below) will be collected at regular intervals before, during and after the infusion period by clinical raters. Blood draws may be conducted at baseline and Time +240 min on V1 and V3 infusion days, as well as at the 24-hour V2 and V4 visits, for a total of six blood draws; however, this is an optional procedure that will occur under a different protocol (GCO 11-1617). On the two infusion days, the blood will be drawn through one of the indwelling catheters that are used for study drug administration.

A urine toxicology screen will be performed before the first infusion and must be negative for illicit substances in order to proceed with the infusion. For females, a urine pregnancy test will confirm non-pregnancy prior to the infusions.

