The **Brief Psychiatric Rating Scale (BPRS)** (Overall and Gorham 1962) is used to assess acute behavioral changes during the infusions. Four key BPRS items for the positive (+) symptoms of psychosis will be used: conceptual disorganization, hallucinatory behavior, suspiciousness, and unusual thought content. Three items representing the negative (-) symptoms of psychosis will also be used: blunted affect, emotional withdrawal, and motor retardation.

The **Clinician-Administered Dissociative States Scale (CADSS)** (Bremner et al. 1998) is used to measure dissociative effects during the infusions. The scale includes 19 questions and 8 observer ratings scored from 0 (not at all) to 4 (extremely). The CADSS measures impairment in body perception, environmental perception, time perception, memory impairment, and feelings of unreality.

Visual Analog Scales. These scales are scored in millimeters from the left-hand side of a 100-mm line to a perpendicular mark made by the patient at a point corresponding to the apparent magnitude of the feeling state. Range: 0 ("not at all") to 100 ("most ever").

Montgomery-Asberg Depression Rating Scale (MADRS) (Montgomery and Asberg 1979). This is a 10-item instrument used for the evaluation of depressive symptoms in adults and for the assessment of any changes to those symptoms. Each of the 10 items is rated on a scale of 0 to 6, with differing descriptors for each item. These individual item scores are added together to form a total score, which can range between 0 and 60 points. The estimated time to administer this scale is 20 minutes. Inter-rater reliability of the scale is high and scores correlate significantly with those of the HAM-D. On the infusion days a modified MADRS will be used that will exclude the sleep and appetite items.

Quick Inventory of Depressive Symptomatology, Self Report (QIDS-SR): The Quick Inventory of Depressive Symptomatology, Self Report (QIDS-SR) is a 16-item self rated instrument designed to assess the severity of depressive symptoms. The 16 items cover the nine symptom domains of major depression as indicated by the DSM, and are rated on a scale of 0-3. Total scores range from 0 to 27, with ranges of 0-5 (normal), 6-10 (mild), 11-15 (moderate), 16-20 (moderate to severe), and 21+ (severe).

Columbia-Suicide Severity Rating Scale (C-SSRS): The Columbia-Suicide Severity Rating Scale (C-SSRS) is a comprehensive, semi-

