The reported incidence of KET-induced perceptual disturbances varies from less than 5% to greater than 30% (Knox et al. 1970; White et al. 1980) and may manifest as vivid dreaming, visualization of psychedelic color, suspension in space, kaleidoscopic floating, and out-of-body experiences. Some patients describe these psychic experiences as bizarre or frightening, while others find them pleasurable, joyful, and fascinating. Indeed, KET is also known as “Special K” as a drug of abuse related to PCP. For that reason KET was placed in Schedule III of the Controlled Substance Act in 1999. Nonetheless, when perceptual disturbances occur, they are usually mild and of short duration (Green and Johnson 1990). KET administration has transient effects on symptoms, usually lasting less than 60 minutes and rarely lasting longer than 2 hours (Carpenter 1999). The perceptual disturbances may be more common in those with preexisting psychosis (Lahti et al. 1995).

Several studies have addressed the question of prolonged psychological effects in the general population secondary to its anesthetic use and concluded that KET does not place patients at a greater risk than other anesthetics (Hersack 1994; Reich and Silvay 1989; Schorn and Witwam 1980). There is no evidence in these long-term studies that individuals exposed to KET are at risk of abusing it on follow-up.

Both ourselves and others have safely used KET in a large number of psychophysiological studies in patients with psychiatric disorders as well as in healthy with doses similar to that of the present study. A meta-analysis of a number of these studies found no evidence of behavioral sensitization following repeated KET exposure (Cho et al. 2005).

7) Provisions for Research Related Injury

We have described above the potential risks of the research procedures and the safeguards that will be used to minimize risks. These include termination of research participation if it is believed that such participation endangers a patient's welfare. Monitoring procedures are used to evaluate potential side effects of treatment or of research procedures. The protocol stipulates an extensive medical and psychiatric evaluation of all patients as a condition for research participation.

 Mount Sinai	Protocol Title:	Pharmacologic attenuation of ketamine using nitroprusside
	Principal Investigator Name/Contact Info:	[name]/ [contact]
	Primary Contact Name/Contact Info	[name] / [contact]
	Date Revised:	4/15/2019

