This study will not include individuals under the age of 21. The rationale for this exclusion is that insufficient data are available in adults to judge the potential risk in children.

15) Multi-Site Human Research (Coordinating Center)

N/A

16) Community-Based Participatory Research

N/A

17) Sharing of Results with Subjects

N/A

18) IRB Review History

N/A

19) Control of Drugs, Biologics, or Devices

 Mount Sinai	Protocol Title:	Pharmacologic attenuation of ketamine using nitroprusside
	Principal Investigator Name/Contact Info:	[name]/ [contact]
	Primary Contact Name/Contact Info	[name] / [contact]
	Date Revised:	4/15/2019
	Study Number:	HSM#16-00928/GCO#16-1580

Note: The IDS has its own forms that must be completed and a review process that must be followed before the IDS representative will sign off on Appendix B for submission to the PPHS.

The pharmacist prepares the IV medication (KET and NP) in a 100 ml NS bag, and a nurse from the GCRC comes to retrieve it the morning of infusion, such that a fixed dose of ml per kg is administered.

At approximately 9 am each patient will begin Infusion 1 (NP or PLC), then 200 minutes later Infusion 2 (KET) will commence. The KET and NP will be stored and dispensed by the research pharmacy.

Anis, N A, S C Berry, N R Burton, and D Lodge. 1983. "The Dissociative Anaesthetics, Ketamine and Phencyclidine, Selectively Reduce Excitation of Central Mammalian Neurones by N-Methyl-Aspartate." *British Journal of Pharmacology* 79 (2): 565–75.

Berman, R M, A Cappiello, A Anand, D A Oren, G R Heninger, D S Charney, and J H Krystal. 2000. "Antidepressant Effects of Ketamine in Depressed Patients." *Biological Psychiatry* 47 (4): 351–54.

Bredt, D S, and S H Snyder. 1989. "Nitric Oxide Mediates Glutamate-Linked Enhancement of cGMP Levels in the Cerebellum." *Proceedings of the National Academy of Sciences of the United States of America* 86 (22): 9030–33.

Bremner, J D, J H Krystal, F W Putnam, S M Southwick, C Marmar, D S Charney, and C M Mazure. 1998. "Measurement of Dissociative States with the Clinician-Administered Dissociative States Scale (CADSS)." *Journal of Traumatic Stress* 11 (1): 125–36. doi:10.1023/A:1024465317902.

Bujas-Bobanovic, M, D C Bird, H A Robertson, and S M Dursun. 2000. "Blockade of Phencyclidine-Induced Effects by a Nitric Oxide Donor." *British Journal of Pharmacology* 130 (5): 1005–12. doi:10.1038/sj.bjp.0703406.

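### Primary outcome (b) is measured from Time 0 to Time 40 minutes, but on the only clock the text defines, ketamine runs from Time 200 to Time 240

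*Combined protocol and SAP*

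**What the plan says.** Section 5(e), Primary Outcomes (b), takes the change in three instruments (the four BPRS positive-symptom items, the CADSS and the VAS): "scores from Time 0 to Time 40 minutes compared across PLC/KET and NP/KET administrations". It does not say what event Time 0 marks.

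Section 5(f), Description of Study Drug Procedures, does define a clock for both infusion days: "At Time 0, Infusion 1 will begin through an infusion pump and will continue until Time 240 minutes". Infusion 1 is nitroprusside (NP) or placebo. The next sentence, which is split by a page header, starts at Time 200 and continues: "minutes, Infusion 2 (KET on both Study Visits 1 and 3) will begin and will continue until Time 240 minutes". Section 19 repeats the lag after Infusion 1 starts: "then 200 minutes later Infusion 2 (KET) will commence".

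On the timing of ratings, section 5(f) says that the BPRS, CADSS and VAS are taken at regular intervals before, during and after the infusion period, and gives no minutes. The instrument descriptions say that the BPRS "is used to assess acute behavioral changes during the infusions" and that the CADSS "is used to measure dissociative effects during the infusions". Under Statistical Analysis in section 5(e): "Data will be analyzed using repeated measures General Linear Models with Time and Treatment Condition as within-subject variables". The levels of Time are not listed. Section 5(f) refers to Table 1 for the events at each visit. That table is not in the text available for this review.

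**The concern.** A primary endpoint window and the dosing clock use the same label, Time 0, and do not fit together. Research Hypothesis II (section 1) concerns psychotomimetic effects right after ketamine, and null hypothesis (b) (section 5(e)) concerns psychotic ratings that ketamine induces. A window that closes before ketamine is given compares NP with placebo alone and says nothing about either.

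The rest of the plan does not repair this. The model's Time factor has no named levels. The BPRS and CADSS wording covers both infusions, so ratings near Time 0 and Time 40 on the section 5(f) clock may exist, and the literal endpoint might be computable.

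The timing of the correction also matters. Section 5(d) plans unblinded interim analyses after 8 and after 16 completers, and the first can end the study. If the window is settled only after someone has seen unblinded results, on three instruments, the choice is open to the charge that the data drove it.

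**Working it through.** **Inputs**

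- Endpoint window: 0 to 40 minutes (section 5(e), outcome (b)).
- Infusion 1: Time 0 to Time 240 (section 5(f)).
- Ketamine: Time 200 to Time 240 (section 5(f)); the start 200 minutes after Infusion 1 begins is repeated in section 19.
- Stated durations: ketamine 40 minutes, NP 240 minutes (section 5(f)).

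**Step 1. Is the section 5(f) clock itself sound?** Duration = end − start.

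- Ketamine: 240 − 200 = 40 minutes, as stated.
- Infusion 1: 240 − 0 = 240 minutes, as stated.

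The clock reproduces both durations and agrees with section 19, so the dosing timetable is not where the slip lies.

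**Step 2. Does the window as written meet ketamine on that clock?** Overlap = max(0, earlier end − later start).

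- Overlap of 0–40 with 200–240: max(0, 40 − 200) = max(0, −160) = 0 minutes.
- Gap from the end of the window to the start of ketamine: 200 − 40 = 160 minutes.

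**Step 3. Which windows would test the hypothesis?** Two candidates end with ketamine.

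| Reading | Window on the section 5(f) clock | Ketamine minutes inside |
|---|---|---|
| As written | 0 to 40 | 0 of 40 |
| Time 0 means ketamine start | 200 + 0 = 200 to 200 + 40 = 240 | 240 − 200 = 40 of 40 |
| Baseline before Infusion 1, end minute misstated | 0 to 240 | 240 − 200 = 40 of 40 |

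**Step 4. Are the two candidates interchangeable?** Let D(t) be the NP/KET minus PLC/KET difference in mean score at Time t.

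- Baseline at Time 200: the contrast is D(240) − D(200).
- Baseline at Time 0: the contrast is D(240) − D(0).
- They differ by [D(240) − D(0)] − [D(240) − D(200)] = D(200) − D(0).

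This difference is whatever NP has done to the ratings in 200 minutes before ketamine. The first contrast subtracts it and the second keeps it. The documents give no value for it. The Background (section 2) reports fewer psychotic phenomena with NP in primary psychotic illness. That is a different population, but the report is reason enough not to assume the term is zero.

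**Step 5. Do the documents choose between the candidates?** The number 40 equals the ketamine duration, which favours the ketamine-start reading. A weaker pointer goes the other way. Section 5(e) says that the blood samples are timed to match clinical ratings, and section 5(f) puts the infusion-day draws at baseline and Time +240. But those draws are optional, fall under another protocol, and their baseline has no minute attached. Neither pointer is decisive.

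**The case against.** The strongest reply is that section 5(e) never adopts the section 5(f) clock. The absence of ketamine from the window follows only when that clock is carried back into the endpoint. The hypotheses, the 40-minute ketamine infusion and the short-lived effect described in section 6 ("KET administration has transient effects on symptoms, usually lasting less than 60 minutes and rarely lasting longer than 2 hours") all indicate that a rating at the end of ketamine was meant. Table 1 may even list the rating minutes.

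Most of this stands. It makes a labelling slip the likely explanation. It does not remove the conflict, because no available passage defines a clock that starts at ketamine. Rating times in Table 1 could show which ratings exist, but the endpoint sentence would still need its anchor. Nor does setting the literal reading aside settle the baseline, as Step 4 shows.

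A reader might infer two stronger things. One is that the trial will really compare NP with placebo before ketamine, or will lack ratings under ketamine. The documents do not support this: section 5(f) plans ratings during and after the infusions, so the fault is in the definition and no loss of data follows from it. The other is that the baseline must be Time 200. The documents do not support that either: no available passage names a rating at Time 200, and a baseline before Infusion 1 fits the hypotheses as well.

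**Conclusion.** The conflict is real and should be corrected. On the only clock in the available text, the window for primary outcome (b) holds 0 of 40 ketamine minutes and ends 160 minutes too early to capture any. As written it cannot test Hypothesis II or null hypothesis (b).

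Confidence is high for the mismatch between sections 5(e) and 5(f), which is simple arithmetic on stated times. It is lower for the cause, where a slip from an undefined ketamine-start clock is the best explanation but remains an inference. It is also lower for any statement about when ratings are taken, because Table 1 could not be read. Which of the two baselines was intended is open, and the size of the difference between them cannot be computed from the documents.

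**What to change.** Before the next unblinded analysis, reconcile outcome (b) with the section 5(f) clock:

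- State outcome (b) in section 5(f) times, with the post-baseline rating at the end of ketamine (Time 240).
- Name the baseline. The candidates are the last rating before ketamine (about Time 200), which subtracts any NP effect already present, and a rating before Infusion 1 (Time 0), which keeps it. The sponsor should choose according to the effect it wants to estimate, without reference to unblinded results, and record the reason.
- Name the same ratings as the levels of the Time factor for outcome (b) under Statistical Analysis.
- If an interim analysis has already been run, state which window it used. The documents do not say whether one has.

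The cost is one sentence in section 5(e) and one clause in the analysis text. If the pre-ketamine baseline is chosen and no rating is scheduled there, a rating time must also be fixed. How the ratings of any patients already treated map onto the named times cannot be settled from these documents.
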